## 21.0 Risks to Subjects

21.1 List the reasonably foreseeable risks, discomforts, hazards, or inconveniences to the subjects related to their participation in the research. Consider physical, psychological, social, legal, and economic risks. Include a description of the probability, magnitude, duration, and reversibility of the risks.

*NOTE: Breach of confidentiality is always a risk for identifiable subject data.*

Response: **Risks Associated with Administration of Intravenous (IV) line, adipose tissue and blood collection:**

All subjects will be informed of the complication of administration of intravenous (IV) line, which includes mild bruising at the site of IV line, which should resolve in few days. They will also be informed about the possibility of infiltration of the IV line at the time of

performing blood draws in which case another IV line at different site will be secured and this may lead to bruising at more than one sites. Fat tissue aspiration will probably lead to a bruise at the site of aspiration. The site will therefore maybe painful for 1-2 weeks. Subjects are advised to call us if they have a lot of pain or swelling at the site after the procedure. Rarely some people have side effects such as low blood pressure or heart rate and allergic reaction to lidocaine including swelling of the throat. Serious risks associated with IV puncture or adipose tissue biopsy may also include infections and thrombosis. If any of these serious side effects is observed, the patients will be asked to call us immediately or seek immediate medical help.

### **Risks Associated with Administration of study drugs:**

All subjects will be referred to Bydureon (extended release exenatide) and dapagliflozin labeling safety information, and will be provided a copy of the package insert of the medication. Discussion of the potential side effects and the different warning and precautions will take place at the time of signing the informed consent and prior to treatment. **Patients will be informed they must not discontinue their insulin during the study.**

Potential side effects of GLP-1 agonist and SGLT-2 inhibitors include hypotension, nausea, polydipsia, polyuria, dehydration, reduced GFR. Patients will be provided guidance on potential side effects and how to properly manage and report it. The potential benefits including improved glycemia, improved BP, potential renal protection, improved quality of life (QOL) will most probably overcome the potential side effects.

Bydureon caused rats to develop tumors of the thyroid gland. Some of these tumors were cancer. It is not known if Bydureon will cause thyroid tumors or a type of thyroid cancer called medullary thyroid cancer in people. This will be discussed in details with all participating subjects. Exenatide is contraindicated in patients with a personal or family history of MTC and in patients with Multiple Endocrine Neoplasia syndrome type 2 (MEN 2).

Injection-site reactions: Serious injection-site reactions, with or without bumps (nodules), have happened in some people who use BYDUREON. Some of these injection-site reactions have required surgical intervention. Report any injection site reactions including nodules to study investigators.

All the known adverse effects with SGLT-2 inhibitors will be discussed with patients before the start of the study as follows:-

- Intravascular volume contraction and symptomatic hypotension can occur after initiating SGLT-2 inhibitors.
- Impairment in Renal Function - SGLT-2 inhibitors increases serum creatinine and decreases eGFR. Elderly patients and patients with impaired renal function may be more susceptible to these changes.
- Genital mycotic Infections - SGLT-2 inhibitors increases the risk of genital mycotic infections. Patients with prior history were more likely to develop genital mycotic infections.

- Bladder Cancer - Across 22 clinical studies, newly diagnosed cases of bladder cancer were reported in 10/6045 patients (0.17%) treated with Dapagliflozin and 1/3512 patient (0.03%) treated with placebo. After excluding patients in whom exposure to study drug was less than one year at the time of diagnosis of bladder cancer, there were 4 cases with dapagliflozin and no cases with placebo. There were too few cases to determine whether the emergence of these events is related to Dapagliflozin.
- The dapagliflozin tablets and matching placebo contain lactose, which may cause discomfort in lactose-intolerant individuals.

There is a risk of DKA, as shown by some studies and by our preliminary data, when SGLT2 inhibitors were used in type 1 diabetes. In our own preliminary studies on triple therapy, we have observed euglycemic ketoacidosis. This has led us to analyze the occurrence of DKA. We found that the patients, who developed DKA, had had their insulin doses reduced to less than or equal to 0.5 units/Kg body weight. Thus, this phenomenon is in part due to insulinopenia and in part due to effects of SGLT2 inhibitors at the hepatic level, which are anti-insulin in nature, like increased gluconeogenesis. On the basis of our data, we shall also not allow the dose of insulin to fall below 0.5 units/Kg body weight. Furthermore, we shall use only the lower dose of dapagliflozin (5mg) in patients who exhibit significant ketonuria with the lower dose.

Severe allergic reaction (anaphylaxis) to study drugs or placebo ingredients or other interventions may accrue in rare cases. Epinephrine is the primary treatment for anaphylaxis with no absolute contraindication to its use. Our site and staff are trained and equipped to assist patients with such reactions. Severe conditions that are not satisfactory managed in site will be transferred to the hospital emergency department for further assessment and help.

*21.2 Describe procedures performed to lessen the probability or magnitude of risks, including procedures being performed to monitor subjects for safety.*

Response:

Safety data (vitals, CBC, CMP, urinary markers) will be collected at screening, during and at end of the study. STAT CMP will be done when glucose or ketones exceeds 400mg/dl and 2.5mM, respectively or any signs of DKA is observed during the acute testing phase. If, ketones measure positive in blood or in urine ( $\geq 0.4$  mM in blood or  $>+1$  in urine) or fasting blood glucose  $<70$  or  $>250$  mg/dl, the acute testing will not take place and patient will be rescheduled. Injection site reactions, mycotic infections and complications of IV and biopsy collection will also be monitored, volume control and hypoglycemia will be monitored and collected at every visit. Physical examination will be performed at 2, 4, 8 and 12 weeks visits and safety assessments performed. Ketone bodies will measured daily by patient in urine. LDL-C levels will be monitored at screening visit, 4 and 12 weeks. Pregnancy will be tested at screening, 4 and 12 weeks. Insulin dose titration will done at every visit to avoid hypoglycemia. Phone calls will be made for safety and compliance follow-up at least 3 time during the study. The patients, however, will be instructed to

report any adverse event or safety related information via phone as soon as it occurs. All safety data will be reviewed by the PI or sub-investigators within 1-2 days of collection.

If the BG concentrations exceed 400 mg/dl or blood  $\beta$ -hydroxybutyrate exceeds 2.5mmol/l (or +3 (80mg/dl) or greater in urine) anytime during the 360 minutes following single dose/doses with no clinical signs and symptoms of DKA like nausea and vomiting then blood sample, spot urine and adipose tissue biopsy will be collected immediately, basal insulin will be restarted; bolus insulin as per the bolus wizard calculator will be administered and a meal provided. Patients will be instructed to come back at the 24-hour mark.

Patients will be instructed to measure ketone bodies in urine samples daily with Ketostix (Bayer) and record it in diary provided. If ketone bodies in urine measure +2 or greater (>4mM in urine), patients are required to notify the research center.

The lower dose of 5 $\mu$ g exenatide will be used for the acute effects testing part of the study. This will help to reduce the risk of GI side effects which commonly happen when first starting exenatide and is increased with the higher dose. Such side effects including nausea, vomiting, diarrhea, feeling jittery, dizziness, headache, acid stomach, constipation, and weakness may lead to, in addition to increase risk and discomfort to patients, increased drop-out rates and erroneous results. This is in part is based on our experience conducting these acute single dose studies.

*21.3 If applicable, indicate **which procedures** may have risks to the subjects that are currently unforeseeable.*

Response:

*Any adverse effects of dapagliflozin or Exenatide not currently known or those unique to their use in Type 1 diabetes may be some of the unforeseeable risks.*

*21.4 If applicable, indicate which research procedures may have risks to an embryo or fetus should the subject be or become pregnant.*

Response: Not applicable, we will not be enrolling pregnant participants or who may become pregnant or with in child baring years without signing the consent stating they will use at least two forms of birth control. If a participant becomes pregnant they will be withdrawn from the study immediately.

*21.5 If applicable, describe risks to others who are not subjects.*

Response: Not applicable, there is no risk to others not participating in this study.

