## 2.0 Scientific Endpoints

2.1 *Describe the scientific endpoint(s), the main result or occurrence under study.*

*NOTE: Scientific endpoints are outcomes defined before the study begins to determine whether the objectives of the study have been met and to draw conclusions from the data. Include primary and secondary endpoints. Some example endpoints are: reduction of symptoms, improvement in quality of life, or survival. Your response should **not** be a date.*

Response:

The study investigations include evaluation of the acute effects of a single dose of dapagliflozin (10mg), exenatide (5µg), a combination of exenatide and dapagliflozin or placebo under insulinopenic condition and the long term effect under basal conditions before and after 12 weeks treatment with dapagliflozin, Exenatide extended release, a combination of Exenatide extended release and dapagliflozin or placebo on ketogenesis, glucagon and lipolysis.

In the acute effects study, qualified patients will come fasting to the research center. Review of study procedures and vitals will be performed. Insulin infusion (pump) will be

stopped and basal blood, urine and adipose tissue biopsy samples will be obtained. Placebos, exenatide (5µg) or dapagliflozin (10mg) (with appropriate placebos) or combination of exenatide and dapagliflozin will be administered, according to a randomized fashion, and blood samples will be collected every 30 min for up to 8 hours after starting the treatment. Urine will be collected every hour up to 8 hours and a second adipose tissue biopsy will be collected at 6 hours after the start of the treatment. Additional blood samples will be collected at 1, 2, 4 and 6 and 8 hour marks for MNC isolation. Plasma and mononuclear cell (MNC) fractions will be prepared from the blood samples. The patient will then come back at the 24 hour mark for a fasting blood and urine collection. The long term study will then commence. Exenatide extended release or dapagliflozin (along with appropriate placebos) or a combination of both drugs will be started and continued for 12 weeks according to original randomization of day 0. In the long term study, dapagliflozin (or the appropriate placebo) will be started at 5mg dose and will be titrated to 10mg/day after 5 days. Fasting blood and 24hr urine samples will be collected at 1, 4 and 8 weeks. At 12 weeks, the 2nd acute effects testing study will be repeated as described above.

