In the acute effects study, qualified patients will come fasting to the research center. Review of study procedures and vitals will be performed. Insulin infusion (pump) will be stopped and basal blood, urine and adipose tissue biopsy samples will be obtained. Placebos, exenatide (5µg) or dapagliflozin (10mg) (with appropriate placebos) or combination of exenatide and dapagliflozin will be administered, according to a randomized fashion and cohort assigned, and blood samples will be collected every 30 min for up to 8 hours after starting the treatment. Urine will be collected every hour up to 8 hours and a second adipose tissue biopsy will be collected at 6 hours after the start of the treatment. Additional blood samples will be collected at 1, 2, 4 and 6 and 8 hour marks for MNC isolation. Plasma and mononuclear cell (MNC) fractions will be prepared from the blood samples. The patient will then come back at the 24 hour mark for a fasting blood and urine collection. The long term study will then commence. Depending on the cohort, Exenatide extended release or dapagliflozin (along with appropriate placebos) or a combination of both drugs will be started and continued for 12 weeks according to original randomization of day 0. In the long term study, dapagliflozin (or the appropriate placebo) will be started at 5mg dose and will be titrated to 10mg/day after 5 days. Fasting blood and 24hr urine samples will be collected at 1, 4 and 8 weeks. At 12 weeks, the 2nd acute effects testing study will be repeated as described above.

Drug Blinding:

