This will now mark the end of the acute testing phase and the beginning of the 12 weeks treatment phase. If the HbA1c is  $\geq 7.5\%$ ; then no reduction will be made in dose of insulin while if the HbA1c ranges from 7-7.5% then the basal and pre-prandial insulin doses will be reduced by 5%. All patients will be instructed on how to give the single subcutaneous injection of Exenatide extended release (2mg weekly) or Exenatide extended release placebo (for those in cohort 1), or open label drugs (for those in cohort 2), which will be administered at home the next day. Patients will also be provided with 12 oral tablets of either 5mg placebo or 5mg dapagliflozin (depending on their group assignment and cohort) and instructed to consume 1 tablet in the morning on each of the first 4 days and 2 tablets (10 mg) on days 5, 6 and 7 (and for the rest of the 12 weeks thereafter) and to return to the center on day 7. Urine collection container will be provided and patients instructed to collect 24hr urine before their next visit. The patients will be trained to recognize the symptoms of DKA and to self-test ketones daily and if they develop any symptoms consistent with DKA, including nausea, vomiting, fatigue, confusion, or shortness of breath. Information sheet about above information will be provided to participants. Patients will be instructed to measure ketone bodies in urine samples daily with Ketostix (Bayer) and record it in diary provided. If ketone bodies in urine measure +2 or greater ( $>4\text{mM}$  in urine), patients are required to notify the research center. The investigators will collect all necessary information and advise the patient of any steps to mitigate the risk of DKA or to visit the closest emergency department and to inform emergency staff of their participation in a research study.

;

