**Visit 3 (Week 1):** Vitals will be measured and fasting blood and 24hr urine samples will be collected. Carbohydrate intake/insulin injection logs, food diaries, or CGM/pump data will be reviewed and documented. Patients will be provided with 3 weeks supply of Exenatide extended release or Exenatide extended release placebo and 10mg dapagliflozin or placebo tablets depending on their cohort. Urine collection container will be provided and patients instructed to collect 24hr urine before their next visit. Insulin doses will be titrated to target blood glucose between 70-180 mg/dl if possible at all times without having additional hypoglycemia (less than 70 mg/dl). Ketostix will be dispensed and patients will be instructed to measure ketone bodies in a spot urine sample daily and reported as described in visit 2.

**Visit 4 (Week 4):** Patient physical and vitals will be measured, fasting blood and 24hr urine samples will be collected. Carbohydrate intake/insulin injection logs, food diaries, or CGM/pump data will be reviewed and documented. Patients will be provided with 4 weeks supply of Exenatide extended release or Exenatide extended release placebo and 10mg dapagliflozin or placebo tablets depending on their cohort. Urine collection container will be provided and patients instructed to collect 24hr urine before their next visit. Insulin doses will be titrated to target blood glucose between 70-180 mg/dl if possible at all times without having additional hypoglycemia (less than 70 mg/dl). Ketostix will be dispensed and patients instructed to measure ketone bodies in a spot urine sample daily and reported as described in visit 3.

**Visit 5 (Week 8):** Vitals will be measured and fasting blood and 24hr urine samples will be collected. Carbohydrate intake/insulin injection logs, food diaries, or CGM/pump data will be reviewed and documented. Patients will be provided with 4 weeks supply of Exenatide extended release or Exenatide extended release placebo and 10mg dapagliflozin or placebo tablets depending on their cohort. Urine collection container will be provided and patients instructed to collect 24hr urine before their next visit. Insulin doses will be titrated to target blood glucose between 70-180 mg/dl if possible at all times without having additional hypoglycemia (less than 70 mg/dl). Ketostix will be dispensed and patients instructed to measure ketone bodies in a spot urine sample daily and reported as described in visit 3.

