**Visit 6 (Week 12):** Subjects will be asked to come for the visit in a fasting state (10-12hr fasting). The will be fasting for the entire visit. Once the patient arrives to the research center, a complete physical examination will be done, 24hr urine will be collected, vitals and fingerstick blood glucose and ketones ( $\beta$ -hydroxybutyrate) using the Precision Extra glucose and ketones meter (Abbott Laboratories) will be measured. For MDI patients, baseline blood, spot urine, and adipose tissue will be collected. The remainder of this visits' procedures apply only to pump patients. An IV port will be placed in order to obtain blood samples throughout the duration of the visit. Insulin infusion will be stopped. Baseline blood, spot urine, and adipose tissue will be collected immediately after stopping insulin. One of the treatment arms will be administered to the patient according to their original group assignment as in Visit 2. All samples and monitoring procedures will be done as in Visit 2. Insulin doses will be titrated to target blood glucose between 70-180 mg/dl if

possible at all times without having additional hypoglycemia (less than 70 mg/dl) before discharge from study.

Phone calls will be made by our team at weeks 2, 6 and 10 to ensure safety. Patients will also be instructed to call if they develop unexpected symptoms.

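### The commitment to keep patients with significant ketonuria on 5 mg dapagliflozin is not carried into the dosing instructions, which step everyone on tablets to 10 mg with no ketone condition

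*Combined protocol and SAP*

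**What the plan says.** The hold appears once, in section 21.1 under the risks of the study drugs: "we shall use only the lower dose of dapagliflozin (5mg) in patients who exhibit significant ketonuria with the lower dose". The same paragraph sets a floor of 0.5 units/kg on the insulin dose. It attaches no test level to significant ketonuria.

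The dosing text reads differently:

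- Section 2.1: "dapagliflozin (or the appropriate placebo) will be started at 5mg dose and will be titrated to 10mg/day after 5 days". Section 10.1 repeats this before the visit descriptions: "will be started at 5mg dose and will be titrated to 10mg/day after 5 days".
- Section 10.1, Visit 2: the patient goes home with 12 tablets of 5 mg (active or placebo), takes one on each of the first four days, then "2 tablets (10 mg) on days 5, 6 and 7 (and for the rest of the 12 weeks thereafter", and is told "to return to the center on day 7".
- Section 10.1, Visits 3, 4 and 5: supply is "10mg dapagliflozin or placebo tablets depending on their cohort", with no alternative for a held patient.
- Section 10.2, schedule table: Visit 3 is on day 8 and is labelled as falling two days after the up-titration, so the step is taken as done.

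Ketone monitoring at home is described under Visit 2 and in section 21.2. Patients test urine daily with Ketostix and must notify the centre at +2 or greater. Investigators then "advise the patient of any steps to mitigate the risk of DKA" or send the patient to an emergency department. For scheduled calls, section 10.1 says "Phone calls will be made by our team at weeks 2, 6 and 10 to ensure safety".

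**The concern.** The safety rule and the dosing rule give different doses to the same patient. Someone who shows ketonuria in the first days on 5 mg should stay there under section 21.1, yet goes to 10 mg under sections 2.1 and 10.1. Staff and patients work from the visit instructions, and those do not mention the hold.

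Diabetic ketoacidosis (DKA) is the hazard that the trial was set up to study, and the step to 10 mg is the point at which the hold is meant to act. If the rule is missed, a patient already showing ketonuria doubles the dose at home. There is a smaller statistical cost. Whether a given patient is held depends on who calls and what is advised, so the regimen compared with placebo on plasma ketones is not fully specified.

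**Working it through.** No sample size or error rate is involved. The check sets the rules side by side and counts days and tablets.

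**1. Does any dosing text carry the hold?**

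| Place | Dose instruction | Ketone condition |
|---|---|---|
| 21.1 | Stay on 5 mg | Significant ketonuria, no level given |
| 2.1 | 10 mg after 5 days | None |
| 10.1, opening text | 10 mg after 5 days | None |
| 10.1, Visit 2 | Two tablets from day 5, at home | None |
| 10.1, Visits 3 to 5 | 10 mg or placebo dispensed | None |
| 10.1, Visit 2, and 21.2 | Dose not mentioned | +2 or greater: notify the centre |

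The home step is stated only under Visit 2. The other dosing passages give the unconditional step without saying where it happens.

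**2. Is there a scheduled staff contact before the step?** The step is on day 5 (Visit 2 text) or day 6 (after five days on 5 mg). Visit 3 is on day 7 (Visit 2 text) or day 8 (schedule table). Days from step to Visit 3:

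- 7 − 6 = 1
- 7 − 5 = 2
- 8 − 6 = 2
- 8 − 5 = 3

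Visit 3 follows the step by 1 to 3 days on every combination. The first phone call is at week 2, and the 24-hour return comes before the long-term treatment starts. Nothing is scheduled during the 5 mg days, the only period in which ketonuria on the lower dose can be seen before the step.

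**3. Which level counts as significant?** The protocol uses three urine levels: above +1 to reschedule acute testing, +2 to notify the centre from home, and +3 as the action level during acute testing. Section 21.1 points to none of them. Only +2 applies to home treatment.

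**4. How many patients could the rule reach?** Section 4.1 puts 15 + 15 = 30 patients on active dapagliflozin in cohort 1. It gives no allocation ratio for the 20 patients in cohort 2. Assuming groups as equal as possible (6, 7 and 7), the two dapagliflozin groups hold 13 or 14, so 43 or 44 take active drug. Adding the 30 cohort 1 patients on placebo tablets, 73 or 74 of 80 take the tablet step. Those affected are the subset with significant ketonuria before it, and the documents give no rate for that.

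**5. Can a hold be supplied?** Section 31.1 lists dapagliflozin only as 5 mg tablets, with a matching placebo in cohort 1, so 10 mg is two tablets. Week 1 as written uses 4 × 1 + 3 × 2 = 10 of the 12 dispensed. A hold uses 7 × 1 = 7.

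**The case against.** The strongest reply is that the texts can be read together. Section 21.1 is a specific and mandatory exception to a general schedule, and staff are bound by both. On that view the defect is a missing cross-reference and an undefined word.

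There is also a working route before the step: daily testing, required notification at +2, and investigators free to advise any mitigating step, which can include staying on one tablet. Section 19.5 asks patients to phone in safety information as it occurs, with same-day review. Section 21.2 has safety data reviewed within one to two days of collection. The patient information sheet promised under Visit 2 is not in the file and may state the rule.

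Much of this stands. A reader might infer that the safeguard is lost, and the documents do not support that: a patient at +2 who calls can be held. But the call leads to no stated dose action, and the step does not wait for it. It is unclear whether the one-to-two-day review covers diary readings that staff have not yet received. Even if the patient sheet carries the rule, the dosing text would still contradict section 21.1.

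A reader might also take the pilot case in section 3.1, where DKA came within 48 hours of the increase to 10 mg, as proof that a missed hold causes DKA. It is not. That patient's insulin had fallen from 0.45 to 0.39 u/kg, and both figures lie below the 0.5 units/kg floor now in section 21.1. No ketone reading on 5 mg is reported, so it cannot be said that the hold would have been triggered.

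**Conclusion.** The conflict is real and should be corrected. Followed as written, the dosing instructions escalate patients whom section 21.1 says to hold, and no scheduled contact falls in the days when the hold would have to be applied.

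Its weight is moderate. An ad hoc hold remains available through the +2 notification and phone reporting, and the insulin floor is a separate protection against DKA. The hold therefore depends on the patient calling and on the investigator applying a rule found only in the risk section.

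The number affected is unknown. The 43 or 44 patients on active drug are an upper bound that rests on near-equal groups in cohort 2. A count of patients at risk would need an assumed ketonuria rate that nothing in the documents supports, and even that count would not be the number harmed. The mismatch between the texts is certain. The practical gap is less so, because the patient sheet cannot be seen.

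**What to change.** - In sections 2.1 and 10.1, including the Visit 2 instructions, and in the patient sheet, make the step conditional. A patient with a Ketostix reading of +2 or greater before the step stays on one tablet and calls the centre. The +2 level is proposed because it is already the home notification level. The investigator may choose another, but it must be stated.
- Define significant ketonuria in section 21.1 by the same level.
- Add a one-tablet branch to dispensing at Visits 3, 4 and 5.
- Apply the rule identically to active and placebo tablets in cohort 1, so that a hold does not reveal the arm.
- Keep held patients in their randomised arm under the intention-to-treat principle in section 17.1.
- As a secondary point, say which dose a held pump patient takes in the Visit 6 acute test.

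The cost is protocol and patient-sheet wording. Tablets, placebo, daily testing and the notification call are already in place, so no new supply or unblinding is needed. If the sheet already states the rule, only the protocol changes.

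The downside is that held dapagliflozin patients receive 5 mg and are likely to be the strongest ketone responders. The dapagliflozin–placebo contrast in plasma ketones, the primary endpoint, may be slightly diluted. Section 21.1 already implies this. If a share f of a dapagliflozin arm is held throughout, its mean daily dose after the step is 10 − 5f mg; f cannot be estimated from the documents.
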